#### **7.3.3. Serious Adverse Events**

All SAEs, regardless of cause or relationship, that occur after the participant first consents to participate in the study (ie, signing the ICF) and throughout the duration of the study, including the posttreatment follow-up visit, must be reported on the applicable CRFs and to PS as instructed below in this section. This also includes any SAEs resulting from protocol-associated procedures performed after the ICF is signed. The investigator must report the primary cause of death for any participant who dies during the follow-up period to the sponsor.

Any SAEs and deaths that occur after the posttreatment follow-up visit but within 30 days of the last dose of study drug, regardless of causality, should also be reported.

Investigators are not obligated to actively seek SAEs after the protocol-defined follow-up period; however, if the investigator learns of any SAEs that occur after the protocol-defined follow-up period has concluded and the event is deemed relevant to the use of study drug, the investigator should promptly document and report the event to PS.

Instructions for reporting SAEs are described in Section [7.4.1](#).

### **7.3.4. Study Drug Special Situations Reports**

All study drug special situations that occur from study drug initiation and throughout the duration of the study, including the posttreatment follow-up visit, must be reported to PS (Section 7.4.2). Adverse events and SAEs resulting from special situations must be reported in accordance with the AE and SAE reporting guidance (Section 7.3).

### **7.3.5. Concomitant Medications Reports**

#### **7.3.5.1. Gilead Concomitant Medications Special Situations Report**

Special situations involving a Gilead concomitant medication (not considered study drug), that occur after the participant first consents to participate in the study (ie, signing of the ICF) and throughout the duration of the study, including the posttreatment follow-up visit, must be reported to PS using the paper SSR (Section 7.4.2.2).

#### **7.3.5.2. Non-Gilead Concomitant Medications Report**

Special situations involving non-Gilead concomitant medications do not need to be reported on the SSR form; however, for special situations that result in AEs because of a non-Gilead concomitant medication, the AE should be reported on the AE CRF.

Any inappropriate use of concomitant medications prohibited by this protocol should not be reported as “misuse,” but may be more appropriately documented as a protocol deviation.

All clinical sequelae in relation to these special situations will be reported as AEs or SAEs at the same time using the AE CRF and/or the SAE CRF. Details of the symptoms and signs, clinical management, and outcome will be reported, when available.

## **7.4. Reporting Process for Serious Adverse Events and Special Situations Reports**

### **7.4.1. Serious Adverse Event Reporting Process**

For fatal or life-threatening events, copies of hospital case reports, autopsy reports, and other documents are also to be transmitted by email or fax when requested and applicable. Transmission of such documents should occur without personal participant identification, maintaining the traceability of a document to the participant identifiers.

Additional information may be requested to ensure the timely completion of accurate safety reports.

Any medications necessary for treatment of the SAE must be recorded onto the concomitant medication section of the participant’s CRF and the SAE narrative section of the Safety Report Form CRF. Results from local laboratory testing done to diagnose and monitor the status of the event should be recorded on the appropriate CRF.

#### 7.4.1.1. Electronic Serious Adverse Event Reporting Process

Site personnel will record all SAE data on the applicable CRFs in order for the SAE information to be transmitted from the CRF to PS within 24 hours of the investigator's knowledge of the event from the time of the ICF signature throughout the duration of the study, including the protocol-required posttreatment follow-up period.

If for any reason it is not possible to record and transmit the SAE information electronically, site personnel must record the SAE on the paper Initial or Follow-up SAE Report Form and transmit by emailing or faxing the report within 24 hours of the investigator's knowledge of the initial event/update using the contact information below.

Gilead Patient Safety:

Email: Safety\[contact]

or

[contact]

If an SAE has been reported via a paper form because the CRF database has been locked, no further action is necessary. If the database is not locked, any SAE reported via paper must be transcribed as soon as possible on the applicable CRFs and transmitted to PS.

#### 7.4.2. Special Situations Reporting Process

##### 7.4.2.1. Electronic Special Situations Reporting Process for Study Drug

Site personnel will record all SSR data on the applicable CRFs and from there transmit the SSR information within 24 hours of the investigator's knowledge to PS from study drug initiation throughout the duration of the study, including the protocol-required posttreatment follow-up period.

If for any reason it is not possible to record and transmit the SSR information electronically, record the SSR on the paper special situations reporting form and submit within 24 hours to:

Gilead Patient Safety:

Email: Safety\[contact]

or

[contact]

If an SSR has been reported via a paper form because the CRF database has been locked, no further action is necessary. If the database is not locked, any SSR reported via paper must be transcribed as soon as possible on the applicable CRFs and transmitted to PS.

See Section 7.4.2.2 for instructions on reporting special situations with Gilead concomitant medications.

#### 7.4.2.2. Reporting Process for Gilead Concomitant Medications

Special situations that involve Gilead concomitant medications that are not considered study drug must be reported within 24 hours of the investigator's knowledge of the event to PS using the paper SSR form and transmitted to:

Gilead Patient Safety:

Email: Safety\[contact]

or

[contact]

Any inappropriate use of concomitant medications prohibited by this protocol should not be reported as "misuse," but may be more appropriately documented as a protocol deviation.

Special situations involving non-Gilead concomitant medications do not need to be reported on the SSR form; however, special situations that result in AEs because of a non-Gilead concomitant medication, must be reported on the AE CRF.

### 7.5. Gilead Reporting Requirements

Depending on relevant local legislation or regulations, including the applicable US Food and Drug Administration CFR, the European Union (EU) Clinical Trials Directive (2001/20/EC)/EU Regulation 536/2014 and relevant updates, and other country-specific legislation or regulations, Gilead may be required to expedite to worldwide regulatory agencies reports of SAEs, which may be in the form of line listings, SADRs, or SUSARs. In accordance with the EU Clinical Trials Directive (2001/20/EC)/EU Regulation 536/2014, Gilead or a specified designee will notify worldwide regulatory agencies and the relevant IEC in concerned Member States of applicable SUSARs as outlined in current regulations.

Assessment of expectedness for SAEs will be determined by Gilead using reference safety information specified in the IB or relevant local label as applicable.

All investigators will receive a safety letter or a quarterly SAE line listing notifying them of relevant SUSAR reports associated with any study drug. The investigator should notify the IRB or IEC of SUSAR reports as soon as is practical, where this is required by local regulatory agencies, and in accordance with the local institutional policy.

### 7.6. Clinical Laboratory Abnormalities and Other Abnormal Assessments as Adverse Events or Serious Adverse Events

Laboratory abnormalities without clinical significance are not to be recorded as AEs or SAEs. However, laboratory abnormalities (eg, clinical chemistry, hematology, urinalysis) that require medical or surgical intervention or lead to study drug interruption, modification, or discontinuation must be recorded as an AE, as well as an SAE, if applicable. In addition, laboratory or other abnormal assessments (eg, electrocardiogram [ECG], x-rays, vital signs) that are associated with signs and/or symptoms must be recorded as an AE or SAE if they meet the

definition of an AE or SAE as described in Sections 7.1.1 and 7.1.2.. If the laboratory abnormality is part of a syndrome, record the syndrome or diagnosis (eg, anemia), not the laboratory result (ie, decreased hemoglobin).

Severity should be recorded and graded according to the DAIDS Table for Grading the Severity of Adult and Pediatric Adverse Events, Toxicity Grading Scale, Version 2.1 {Division of AIDS 2017}. For AEs associated with laboratory abnormalities, the event should be graded based on the clinical severity in the context of the underlying conditions; this may or may not be in agreement with the grading of the laboratory abnormality.

The DAIDS scale is available at:

<https://rsc.niaid.nih.gov/sites/default/files/daidsgradingcorrectedv21.pdf>

## 7.7. Toxicity Management

All clinical and clinically significant laboratory toxicities will be managed according to the guidelines described below.

The Gilead medical monitor should be consulted prior to study drug discontinuation when medically feasible. Before discontinuation of study drug for AEs or laboratory abnormalities, an assessment of the participant's medical situation should be made by the investigator.

### 7.7.1. Laboratory Events Meeting Discontinuation Criteria

Laboratory events meeting discontinuation criteria are discussed in Section 3.3.1.1.

### 7.7.2. Grades 1 and 2 Laboratory Abnormality or Clinical Event

Continue study drug at the discretion of the investigator.

### 7.7.3. Grades 3 and 4 Laboratory Abnormality or Clinical Event

For a clinically nonsignificant Grade 3 or higher laboratory abnormality, study drug may be continued without dose interruption.

For a clinically significant Grade 3 or higher laboratory abnormality, confirmed by repeat testing, or clinical event, **that is considered to be related to the study drug, the participants will be discontinued from the study drug.** The participant should be managed according to local practice. The participant should be followed as clinically indicated until the laboratory value returns to baseline or is otherwise explained, whichever occurs first, or until the clinical event resolves or stabilizes.

For a clinically significant Grade 3 or higher laboratory abnormality or clinical event, study drug may be continued if the event is considered to be unrelated to study drug.

All Grade 3 or higher laboratory abnormalities occurring by Day 10, regardless of clinical significance, should be retested until they have resolved or returned to baseline levels, or they are considered irreversible, or until there is a satisfactory explanation for the changes observed.

A clinically significant Grade 3 or higher laboratory abnormality that is not confirmed by repeat testing should be managed according to the algorithm for the new toxicity grade.

Recurrence of laboratory abnormalities considered unrelated to study drug may not require permanent discontinuation but requires discussion with the Gilead medical monitor.

Grade 3 and Grade 4 treatment-emergent toxicities will be noted by the investigator and brought to the attention of the Gilead medical monitor, and the appropriate course of action will be discussed and decided. Whether or not considered treatment-related, all participants experiencing Grade 3 and Grade 4 AEs must be monitored periodically until symptoms subside, and any Grade 3 or Grade 4 abnormal laboratory values should be retested until they have resolved or returned to baseline levels, or they are considered irreversible, or until there is a satisfactory explanation for the changes observed.

Any questions regarding toxicity management should be directed to the Gilead medical monitor.

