### **3.3. Protocol-Specific Discontinuation Criteria**

#### **3.3.1. Criteria for Early Discontinuation for the Individual Participant**

##### **3.3.1.1. Criteria for Early Discontinuation From Study Intervention**

Study intervention will be discontinued in the following instances:

- Any serious adverse event (SAE) suspected to be related to study drug.
- Any Grade 3 or higher AE suspected to be related to study drug.
- An AE or worsening of clinical condition requiring clinical intervention, that would, in the judgment of the investigator, affect assessments of clinical status to a significant degree.
- Unacceptable toxicity, as defined in Section [7.7](#), or toxicity that, in the judgment of the investigator, compromises the ability to continue study-specific procedures or is considered not to be in the participant's best interest.
- Caregiver request to discontinue for any reason (Section [3.3.1.1.1](#)).
- Participant noncompliance.

- Any Grade 3 or higher clinically significant laboratory abnormality (if confirmed by repeat testing) suspected to be related to study drug.
- Alanine aminotransferase (ALT)  $\geq 5 \times$  upper limit of normal (ULN).
- Participants  $\geq 1$  year of age who have a confirmed eGFR  $< 80$  mL/min/1.73 m^2 by bedside Schwartz formula.
- Participants  $< 1$  year of age who have a confirmed creatinine level above the ULN as defined by the local laboratory and appropriate for the GA and chronological age.

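### Protocol Section 3.3.1.1 requires study drug to stop for two kinds of clinical event for which Sections 7.7.2 and 7.7.3 let it continue, and no text says which section prevails

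*Protocol*

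**What the plan says.** Protocol Section 3.3.1.1 lists ten criteria under a mandatory lead-in, "Study intervention will be discontinued in the following instances". The first is "Any serious adverse event (SAE) suspected to be related to study drug", with no grade limit. The second is "Any Grade 3 or higher AE suspected to be related to study drug". The third covers an AE or clinical worsening that requires intervention and that the investigator judges would affect assessment of clinical status to a significant degree. It has no limit on grade or on relatedness.

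Section 7.7 is equally directive: "All clinical and clinically significant laboratory toxicities will be managed according to the guidelines described below". Its subsections then say:

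- 7.7.1: "Laboratory events meeting discontinuation criteria are discussed in Section 3.3.1.1".
- 7.7.2, for Grade 1 and 2 laboratory abnormalities and clinical events: "Continue study drug at the discretion of the investigator".
- 7.7.3, for Grade 3 or higher: study drug stops for a related clinical event, or for a related, clinically significant laboratory abnormality confirmed on repeat. For an unrelated event, laboratory or clinical, "study drug may be continued if the event is considered to be unrelated to study drug".

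Neither 7.7.2 nor 7.7.3 makes an exception for events listed in 3.3.1.1.

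**The concern.** Both sections tell the site what to do with study drug, and for some clinical events they give different answers. A site that keeps a child on drug under 7.7 follows that section as written and breaches 3.3.1.1. Two sites could therefore handle the same event differently, each able to cite the protocol.

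Participants are under 5 years of age and receive an investigational drug. Section 1.5 counts clearly set discontinuation parameters among the measures that reduce risk, so the protocol's own benefit-risk case relies on this text being unambiguous.

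**Working it through.** No arithmetic beyond a count applies. Each toxicity-related criterion in 3.3.1.1 is set beside the rule that 7.7.2 or 7.7.3 gives for the same event, then checked against the 7.7.1 pointer.

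| Event | 3.3.1.1 | 7.7.2 / 7.7.3 | Reached by 7.7.1? | Result |
|---|---|---|---|---|
| Related SAE, Grade 1–2 | Stop | 7.7.2: investigator's discretion | No, clinical | Conflict |
| AE or worsening needing intervention and significantly affecting assessment, Grade 1–2 | Stop | 7.7.2: investigator's discretion | No, clinical | Conflict |
| The same, Grade 3 or higher, unrelated | Stop | 7.7.3: may continue | No, clinical | Conflict |
| Related AE, Grade 3 or higher | Stop | 7.7.3: stop | Not needed | Agree |
| Related, confirmed, clinically significant laboratory abnormality, Grade 3 or higher | Stop | 7.7.3: stop | Not needed | Agree |
| ALT, eGFR and creatinine thresholds | Stop | Graded rules, read alone, could allow continuation | Yes | Resolved by the pointer |

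**Can a related SAE be Grade 1 or 2?** Section 7.1.2 defines seriousness by outcome, such as hospitalization or a medically important event. Section 7.2.2 grades severity separately, on the DAIDS scale. Section 3.3.1.1 also lists related SAEs and related AEs of Grade 3 or higher as separate criteria. If every related SAE were Grade 3 or higher, the first criterion would add nothing to the second. The protocol's own structure therefore allows for the case.

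**Do the two tests in the third criterion's case coincide?** No. Section 3.3.1.1 asks whether the event needs intervention and would significantly affect assessment. Section 7.7.3 asks whether it is related to study drug. Worsening RSV illness judged unrelated to drug could meet the first test and also qualify for continuation under the second.

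**Count.** Of the ten criteria:

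- 2 conflict with no pointer (related SAE; AE or worsening needing intervention).
- 3 are laboratory thresholds reached by 7.7.1.
- 2 agree in both sections.
- 1 is unacceptable toxicity, which 3.3.1.1 says is defined in 7.7. That term does not appear there.
- 2 are not toxicity rules (caregiver request; noncompliance).

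2 + 3 + 2 + 1 + 2 = 10.

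**The case against.** The best defence is that the rules can be followed together. The wording in 7.7.2 and 7.7.3 is permissive and that in 3.3.1.1 is mandatory, so a site that stops drug satisfies both, and a general permission need not cancel a specific stop. This holds for a site that reads both sections and stops. It does not help a site that works from 7.7, which claims to govern all clinical toxicities and mentions no exception for the clinical events on the list.

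A second defence is that the intervention criterion already rests on the investigator's judgment, so some variation between sites would survive any rewording. That stands, and it makes this the softer of the two conflicts. But the judgment concerns the effect on assessment; once it is made, 3.3.1.1 requires a stop while 7.7 still leaves the choice open.

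A third is central oversight. SAEs reach Patient Safety within 24 hours (7.4.1.1), the medical monitor should be consulted before discontinuation where feasible (7.7), and Grade 3 and 4 toxicities are discussed with the monitor (7.7.3). These reduce the risk. None sets precedence, and the required discussion of the course of action does not extend to a Grade 1 or 2 related SAE for which the site simply continues drug.

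A reader might also count the ALT, eGFR and creatinine stops, including the one for infants "who have a confirmed creatinine level above the ULN", as conflicts, giving five of ten. The documents do not support that. Section 7.7.1 comes before the graded rules, is headed for exactly these events, and sends the reader to 3.3.1.1. Nor is the unacceptable-toxicity reference empty: the emphasized stop rule in 7.7.3 largely supplies its content, though not under that name.

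**Conclusion.** The protocol contradicts itself for two clinical-event criteria: a related SAE of Grade 1 or 2 (3.3.1.1 against 7.7.2), and an AE or worsening needing intervention that would significantly affect assessment of clinical status (3.3.1.1 against 7.7.2 at Grade 1 or 2, and against 7.7.3 at Grade 3 or higher when unrelated). It should be corrected because it bears on whether a young child stays on an investigational drug.

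The conclusion rests on two assumptions: that the DAIDS table, which the protocol cites but does not reproduce, does not place every serious event at Grade 3 or higher; and that no site instruction outside these documents sets precedence. Different handling between sites is a possibility inferred from the text. The documents report no such case and give no frequency for either event.

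A reader might infer that the efficacy results are affected. They are not to any material degree. The primary estimand handles treatment discontinuation by treatment policy, SAP Section 6.1.2 ignores it in the derivation, and SAP Section 6.3 limits efficacy to descriptive summaries after early termination. The output most directly exposed is the summary and listing of AEs leading to premature discontinuation of study drug (SAP Section 7.1.6), which could partly reflect which section a site followed.

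**What to change.** Reconcile 3.3.1.1 with 7.7.2 and 7.7.3 so that one rule applies to each of the two criteria, and state which section takes precedence for clinical events, as 7.7.1 in effect does for laboratory events. Make the unacceptable-toxicity reference in 3.3.1.1 point to identifiable text in 7.7. Which rule stands is for the sponsor's clinical team; this review takes no position on it.

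The cost is protocol wording and a clarification to sites, with no added visits, samples or participants. Because the SAP reports early termination, the change may have little prospective use in this study. If dosing has ended, the study report can state which section was applied when drug discontinuations are listed, and the wording can be corrected before the text is reused.

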## 8. STATISTICAL CONSIDERATIONS

This section provides a high-level description of the planned analyses, assessed statistical power with assumptions, and any applicable multiplicity adjustments. Additional details of the statistical methods will be provided in the statistical analysis plan (SAP), including any deviations from the original statistical analyses planned.

### 8.1. Analysis Objectives and Endpoints

Objectives and endpoints are listed in Section 2.

#### 8.1.1. Primary Endpoint

The primary efficacy endpoint is time to alleviation of targeted RSV symptoms by Day 28.

For nonhospitalized participants, alleviation of targeted RSV symptoms is defined as:

- Improvement in score by at least 1 point reported at 2 daily consecutive assessments (ie, 24-hour period) for any targeted RSV symptom for which the baseline score is  $> 1$  (ie, ranging from very mild to very severe)
- No increase in score reported at 2 daily consecutive assessments (ie, 24-hour period) for any targeted RSV symptom for which the baseline is 1 (ie, no symptom)

The date of the first day of the 2 daily consecutive assessments will be considered the time of alleviation of targeted RSV symptoms. Note: GRCD is collected twice daily as both daytime and overnight symptoms are assessed.

Targeted RSV symptoms refers to the RSV symptoms included in the GRCD global composite score (cough, respiratory signs, RSV signs, behavior impact) assessed by GRCD.

#### 8.1.2. Secondary Endpoints

##### 8.1.2.1. Time to Sustained Alleviation of Targeted RSV Symptoms by Day 28

For nonhospitalized participants, sustained alleviation of targeted RSV symptoms is defined similarly to alleviation of targeted RSV symptoms but for 3 daily consecutive assessments (ie, 48-hour period).

##### 8.1.2.2. Time to Resolution of Targeted RSV Symptoms by Day 28

For nonhospitalized participants, resolution of targeted RSV symptoms is defined as:

- Improvement in score resulting in score of  $\leq 2$  (ie, no symptom or very mild) reported at 2 daily consecutive assessments (ie, 24-hour period) for any targeted RSV symptom for which the baseline score is  $> 2$  (ie, ranging from mild to very severe)

- No increase or an improvement in score resulting in score of  $\leq 2$  (ie, no symptom or very mild) reported at 2 daily consecutive assessments (ie, 24-hour period) for any targeted RSV symptom for which the baseline score is 2 (ie, very mild)
- No increase in score reported at 2 daily consecutive assessments (ie, 24-hour period) for any targeted RSV symptom for which the baseline score is 1 (ie, no symptom)

The date of the first day of the 2 daily consecutive assessments will be considered the time of resolution of targeted RSV symptoms. Note: GRCD is collected twice daily as both daytime and overnight symptoms are assessed.

Targeted RSV symptoms refers to the RSV symptoms included in the GRCD global composite score (cough, respiratory signs, RSV signs, behavior impact) assessed by the GRCD.

